10.5. Study Drug Accountability

The investigator is required to maintain adequate records of the disposition of the study drug, including the date and quantity of drug received, to whom the drug was dispensed (participant-by-participant accounting), and a detailed accounting of any drug accidentally or deliberately destroyed. Records for receipt, storage, use, and disposition will be maintained by the study site. A study drug dispensing log will be kept current and will include identification of each participant and the date and quantity of study drug dispensed. All records regarding the disposition of the study drug will be available for inspection by the study monitor and BARDA.

10.6. Study Drug Handling and Disposal

After dosing has been completed for all participants, to satisfy regulatory requirements regarding accountability, all study drug will be reconciled and destroyed according to applicable regulations. Study drug will not be destroyed until authorized in writing by BARDA.

10.7. Randomization and Blinding

10.7.1. Randomization

Participants 18 through 65 years of age, inclusive, will be randomized 1:1 to one of two treatment dosing sequences (A or B) as specified in [Table 3](#). The randomization schedule will be generated by the statistical team at Rho using a web-based randomization system.

10.7.2. Blinding

This study is not blinded.

11. ASSESSMENT OF PHARMACOKINETICS

Blood samples will be collected from each participant for PK assessments by a designated, qualified individual from the study research team. At Visit 1 (Day 1) and Visit 2 (Day 8), an indwelling venous catheter will be placed before dose administration for blood sample collection for serial determinations at the following times: 0 (pre-dose) and at 13 time points post-dose at 5, 10, 15, 20, 30, 45, 60, and 90 minutes, and 2, 2.5, 4, 6, and 8 hours. Ten (10) mL of whole blood will be collected into a sterile vacutainer containing ethylenediaminetetraacetic acid (EDTA) as a preservative for each sampling. Plasma will be stored frozen until analysis.

Pharmacokinetic samples will be analyzed by a bioanalytical facility approved by BARDA.

12. ASSESSMENT OF SAFETY

12.1. Safety Parameters

Safety will be evaluated utilizing the assessments defined in this section. If deemed clinically necessary, additional safety assessments not currently specified in the protocol may be performed at the discretion of the site investigator in consultation with the medical monitor and BARDA.

12.1.1. Demographic/Medical History

In order to define a baseline for potential AEs, the demographics and medical history of each participant will be collected at the Screening Visit.

12.1.2. Vital Signs

Vital sign measurements, including oral temperature, heart rate, respiratory rate, and diastolic and systolic blood pressure (after the participant is seated for at least 5 minutes), will be collected at Screening, Visit 1 (Day 1 Pre-dose), and Visit 2 (Day 8 Pre-dose) prior to any blood draws. Post-dose automated blood pressure and heart rate measurements will be recorded on the opposite arm from blood collection every 15 ± 5 minutes for the first hour, every 20 ± 5 minutes for the second hour, and every 30 ± 5 minutes for the third and fourth hours and thereafter as deemed clinically necessary by the investigator until the end of each visit. Vital signs may be repeated at an Unscheduled or Early Termination (ET) Visit per the investigator's discretion.

Respiratory rate, if regular, may be assessed over 30 seconds and doubled, but in no case will it be assessed over a period of less than 30 seconds. If the respiratory rate is irregular, it will be assessed over 60 seconds.

12.1.3. Weight and Height

Participant's height and weight will be measured at the Screening Visit. Body mass index (BMI) will be derived automatically from height and weight measurements in the electronic data capture system. Participant's weight will be assessed again at Visit 1 (Day 1 Pre-dose) and Visit 2 (Day 8 Pre-dose). Weight may be measured at an Unscheduled or ET Visit per the investigator's discretion.

12.1.4. Physical Examination

A physical examination will be performed at the Screening Visit to assess and confirm eligibility. The examination will include a general assessment of the skin, head, ears, eyes, nose, throat, neck, oral cavity, thyroid, lungs, heart, abdomen, lymph nodes, and musculoskeletal system/extremities, and a neurological (cranial nerve examination, including pupillary diameter, eye movements, and deep tendon reflexes) examination. A symptom-based physical examination may be performed at dosing visits, or at an Unscheduled or ET Visit per the investigator's discretion. In general, clinically significant abnormal findings are expected to be associated with an item recorded in the participant's medical history (when detected at Screening) or as an AE (when detected after Screening).

12.1.5. Electrocardiogram (ECG)

A standard 12-lead ECG will be recorded and assessed at the Screening Visit, Visit 1 (Day 1 Pre-dose), and Visit 2 (Day 2 Pre-dose). Additionally, an ECG may be performed for any complaints of chest discomfort, lightheadedness, and/or palpitations per the investigator's discretion and repeated as needed during Visit 1 (Day 1 Post-dose) and Visit 2 (Day 2 Post-dose). ECGs may also be performed at an Unscheduled or ET Visit per the investigator's discretion. ECGs will be reviewed by a medically qualified individual to verify whether any abnormalities are clinically significant. In general, clinically significant abnormal ECGs are expected to be associated with an item recorded in the participant's medical history (when detected at Screening) or as an AE (when detected after Screening).

12.1.6. Clinical Laboratory Assessments

At the Screening Visit, venous blood and urine will be collected for all participants for Screening laboratory assessments. All clinical laboratory assessments provided in this section will be performed at Screening.

Clinical laboratory assessments may be repeated at an Unscheduled or ET Visit as clinically indicated per the investigator's discretion.

Samples will be analyzed by the local lab. The details for sample handling, processing, and shipping will be provided in the Laboratory Manual. Individual results will be sent to the clinical site, and the investigator will perform a clinical assessment of all laboratory data to assess eligibility and identify and document AEs as applicable.

The clinical laboratory assessments planned for this study are as follows:

12.1.6.1. Complete blood count with differential

[Table 5](#) lists the parameters of the complete blood count with differential.

Table 5: Complete Blood Count with Differential

Red blood cells	White blood cells
Hematocrit	Basophils (% and absolute count)
Hemoglobin	Eosinophils (% and absolute count)
Red blood cell count	Lymphocytes (% and absolute count)
Platelets	Monocytes (% and absolute count)
Platelet count	Neutrophils (% and absolute count)
	White blood cell count

12.1.6.2. Serum Chemistry, Liver Function, and Thyroid-stimulating Hormone Assessments

The clinical chemistry, liver function, and TSH assessments planned for this study are provided in [Table 6](#):

Table 6: Serum Chemistry, Liver Function, and TSH Assessments

Chem 7 panel
Blood urea nitrogen (BUN)Carbon dioxideCreatinineGlucoseSerum chlorideSerum potassiumSerum sodium	
Liver function tests (LFTs);
Aspartate aminotransferase (AST)Alanine transaminase (ALT)Alkaline phosphatase (ALP)Direct bilirubinTotal bilirubin (fractionated for values for total bilirubin > ULN)Thyroid-stimulating hormone (TSH) with reflex to T4
----------------------------------------------------------------------------------------------------------------------------------------------------------------------------------------------------------------------------------------------------------------------------	----------------------------------------------------------------------------------------------------------------------------------------------------------------------------------------------------------------------------------------------------------------------------------------------------------------------------------------------------------------------------------------------------------------------

12.1.6.3. Virus Serology

At the Screening Visit, participant medical history will be reviewed for known human immunodeficiency virus (HIV) infection, and acute or chronic hepatitis B or hepatitis C infection. In addition, blood samples will be collected at the Screening Visit for HIV, hepatitis B surface antigen (HBsAg), and hepatitis C antibody (anti-HCV) tests.

12.1.6.4. Urine Drug Screen

A urine drug screen will be performed at the Screening Visit and will include tests for amphetamines, cocaine, tetrahydrocannabinol, methylenedioxymethamphetamine, and opiates.

12.1.6.5. Pregnancy Screen

At the Screening Visit, blood will be collected for a serum quantitative beta-human chorionic gonadotropin (beta-HCG) assay for female participants of childbearing potential. At Visit 1 (Day 1 Pre-dose) and Visit 2 (Day 8 Pre-dose), a urine point-of-care (POC) pregnancy test will be performed onsite for female participants of childbearing potential.

Additionally, a urine POC pregnancy test will be performed at any time during study participation if pregnancy is suspected.

12.1.7. Adverse Event Assessment

At all visits and phone contacts, including an ET or Unscheduled Visit, site staff will ask nonleading questions regarding the participant's health status (Section 12.3.1) and document any new or changed AEs. Adverse events occurring during washout periods (i.e., between Visit 1 and Visit 2, and between Visit 2 and the Telephone Follow-up Visit) should be collected at the next participant contact.

12.1.8. Concomitant Medication Assessment

Site staff will review concomitant medications (Section 9.2) at Screening, as well as Visit 1 (Day 1 Pre-dose) and Visit 2 (Day 8 Pre-dose) prior to administration of study drug. On Visit 1 (Day 1 Post-dose) and Visit 2 (Day 8 Post-dose), any medications or treatments administered to the

participant during attendance at the Clinical Research Unit (CRU) will also be recorded. Concomitant medications will also be reviewed during the Follow-Up telephone contact and at an Unscheduled or ET Visit.

12.2. Adverse and Serious Adverse Events

12.2.1. Definition of Adverse Events

12.2.1.1. Adverse Event (AE)

An AE is any untoward medical occurrence associated with the use of a drug in humans, whether or not it is considered drug related [21 Code of Federal Regulations [CFR] 312.32(a)]. An AE can therefore be any unfavorable and unintended sign (including an abnormal laboratory finding), symptom, or disease temporally associated with the use of a medicinal (investigational) product, whether or not related to the medicinal (investigational) product (Integrated Addendum to International Council for Harmonisation [ICH] E6[R1]: Guideline for Good Clinical Practice [GCP] E6[R2]).

Laboratory results and vital sign excursions of any magnitude will be defined as AEs if they are considered clinically significant by the site investigator. A lab or vital sign result should generally be considered clinically significant and an AE if, regardless of degree out of range, it has a reasonable probability of reflecting or contributing to a disturbance of homeostasis or pathological process or outcome.

Suspected adverse reaction (SAR) means any AE for which there is a reasonable possibility that the drug caused the event. For the purposes of safety reporting, “reasonable possibility” means there is evidence to suggest a causal relationship between the drug and the AE. A SAR implies a lesser degree of certainty about causality than adverse reaction, which means any AE caused by a drug [21 CFR 312.32(a)].

An AE or SAR is considered “unexpected” if it is not listed in the package inserts for the study drugs or is not listed at the specificity or severity that has been observed.

12.2.1.2. Serious Adverse Event (SAE)

An AE or SAR is considered “serious” if, in the view of either the site investigator or BARDA, it results in any of the following outcomes [21 CFR 312.32(a)]:

- Death
- Life-threatening adverse event that in the view of the site investigator or BARDA, places the participant at immediate risk of death. This does not, however, include an event that, had it occurred in a more severe form, might have caused death.
- Requires inpatient hospitalization or prolongs existing hospitalization. Planned hospitalizations will not be reported as SAEs unless categorized as medically important. Emergency room visits and observational admissions of under 24 hours, in themselves, do not qualify as SAEs.
- Results in persistent or significant disability/incapacity or substantial disruption of the ability to conduct normal life functions.

- Congenital anomaly/birth defect.
- Important medical events that may not result in death, be life threatening, or require hospitalization may be considered a serious adverse drug experience, when based on appropriate medical judgment, they may jeopardize the participant, or the participant may require medical or surgical intervention to prevent one of the outcomes listed in this definition.

12.3. Collection, Recording, and Grading Severity of Adverse Events

12.3.1. Collection of Adverse Events

Adverse events of any type described above may be discovered through a variety of methods:

- Observing the participant
- Questioning the participant with standard nonleading questions to elicit any medically related changes in their well-being (e.g., Have you been hospitalized, had any accidents, used any new medications, or changed any medications [both prescription and OTC]?)
- Receiving an unsolicited complaint from the participant
- An abnormal value or result from a clinical (e.g., vital signs) or laboratory evaluation

12.3.2. Recording Adverse Events

Throughout the study, the investigator will record AEs on the eCRF. SAEs must be reported to Rho pharmacovigilance personnel within 1 business day of the site's awareness of the event. For the purposes of this study, any detrimental change in the participant's condition after signing informed consent and up to completion of the follow-up period after the last administration of study drug (i.e., through Follow-up [Day 15]) will be considered an AE and must be recorded. Treatment-emergent AEs are defined as AEs occurring after the participant receives at least one dose of atropine. AEs will be followed per the below criteria:

- AEs judged at least possibly related to study drug will be followed to resolution (with or without sequelae) or until considered stable by the investigator (in consultation with the medical monitor in situations of uncertainty).
- AEs judged unrelated to study drug will be followed to resolution (with or without sequelae) or, if not resolving, until considered stable by the investigator (in consultation with the medical monitor in situations of uncertainty), or until the end of the participant's study participation, whichever comes first.

12.3.3. Grading Severity of Adverse Events

The severity of AEs and SAEs will be graded as defined by criteria set forth in the NCI-CTCAE Manual Version 5.0. AEs will be graded on a scale from 1 to 5 according to the following standards in the NCI-CTCAE manual:

Grade 1 = mild AE

Grade 2 = moderate AE

Grade 3 = severe AE

Grade 4 = life-threatening AE or urgent intervention indicated

Grade 5 = death

Events grade 1 or higher will be recorded on the appropriate AE eCRF for this study.

It is important to distinguish between serious and severe AEs. Severity is a measure of intensity, whereas seriousness is defined by the criteria in Section [12.2.1.2](#).

12.4. Relationship and Attribution to Study Drug

An investigator's causality assessment is the determination of whether there exists a reasonable possibility that the study drug caused or contributed to an AE and must be provided for all AEs (serious and non-serious). The site investigator will assess and record the causality/relationship between the study drug and the AE.

BARDA's determination of attribution will be used for reporting to the IRB.

The relation and attribution of an AE to study drug will be determined using the descriptors and definitions provided in [Table 7](#).

Table 7: Attribution of Adverse Events

Unrelated Categories	
Not Related	The AE is clearly not related to study drug.
Unlikely Related	The AE is unlikely related to study drug.
Related categories	
Possibly Related	The AE has a reasonable possibility to be related to study drug; there is evidence to suggest a causal relationship.
Probably Related	The AE is likely related to study drug.
Related	The AE is clearly related to study drug.

AE = adverse event

12.5. Reporting Safety Events to IRB

Once AEs and SAEs are recorded, Rho pharmacovigilance personnel will collaborate with appropriate personnel from BARDA and Allucent to process events and report events in a timely fashion to the IRB in accordance with applicable regulations and guidelines. Procedures for AE processing and reporting are detailed in the Data Safety Monitoring Plan (DSMP).

12.6. Pregnancy Reporting

This study includes pregnancy as safety data. Although pregnancy is not an SAE, information about any pregnancy in a female study participant should be reported to Rho pharmacovigilance personnel within 1 business day of the site's awareness of the event for tracking purposes.

Study dose administration will be discontinued for the pregnant participant. The investigator shall counsel the pregnant participant and discuss the risks of continuing with the pregnancy and

the possible effects on the fetus. Monitoring of the pregnant participant shall continue until the conclusion of the pregnancy.

The pregnancy will be documented when identified and at its conclusion.

Should pregnancy result in a congenital abnormality, birth defect, miscarriage, or medically indicated abortion, an SAE must be submitted to Rho using the SAE reporting procedures described in Section [12.3.2](#).

12.7. Reporting Other Safety Information

Site investigators should promptly notify Rho, Allucent, BARDA, and the IRB when an unanticipated problem involving risks to participants or others, which is not otherwise reportable as an AE, is identified.

13. STATISTICS

13.1. Endpoints

Endpoints are summarized in [Table 2](#) under Section [6](#).

The bioequivalence of atropine sulfate administered SL versus administered IM as measured by the following PK parameters using noncompartmental analysis (NCA) methods:

- Area under the analyte concentration versus time curve to infinity (AUC_{∞})
- Area under the analyte concentration versus time curve to time of last quantifiable data point (AUC_{t_f})

The relative bioavailability of atropine sulfate administered SL versus IM as measured by the following PK parameters using NCA methods:

- Area under the analyte concentration versus time curve to 45, 60, 90, 120, 150, and 240 minutes (AUC_{45} , AUC_{60} , AUC_{90} , AUC_{120} , AUC_{150} , and AUC_{240} , respectively)
- Maximum measured plasma concentration (C_{max})
- Time to C_{max} (t_{max})
- Apparent terminal elimination half-life ($t_{1/2}$)
- Terminal elimination rate constant (λ_z)
- Volume of distribution (V_d/F)
- Total body clearance (CL/F)
- Absorption rate constant (K_a)

13.1.1. Measures to Minimize Bias

Permuted block randomization will be performed centrally by designated Rho staff and will balance enrollment between treatment dosing sequences (see Section [10.7](#) for more details).

13.1.2. Analysis Plan

Statistical analyses will be performed using SAS® software Version 9.4 or later. Phoenix WinNonLin Version 8.3 software will be used to generate PK parameter estimates.

Descriptive statistics will be used to summarize participant characteristics and safety. These summaries will be presented overall and separately for each route of administration.

Details of the statistical analyses, methods, and data conventions will be described in the Statistical Analysis Plan (SAP).

13.1.2.1. Analysis Populations

13.1.2.1.1. PK Analysis Population

The PK analysis population will include all participants who are randomized, receive at least 1 study drug dose, and have PK samples collected for that period. Each participant's data will be

analyzed according to the corresponding route of administration for the applicable period. The PK analysis population will be used for all PK analyses.

13.1.2.1.2. Per Protocol Population

The per protocol population will include all participants who are randomized, receive atropine via both routes of administration according to their randomized dosing sequence, and have PK samples collected for both periods. In addition, participants with major protocol deviations may be excluded if it is determined that the deviations affect the integrity of PK data. Each participant's data will be analyzed according to the corresponding route of administration for the applicable period. Primary and secondary analyses will be repeated in the per protocol population if it differs from the PK analysis population.

13.1.2.1.3. Safety Population

The safety population will include all participants who are randomized and receive at least 1 study drug dose. Each participant's data will be analyzed according to the corresponding route of administration for the applicable period. The safety population will be used for all safety displays.

13.1.2.2. Primary Analysis

Pharmacokinetic parameters AUC_{∞} and AUC_t will be estimated for each participant and route using the noncompartmental method and will be summarized by route of administration using descriptive statistics.

Relative bioavailability of SL administration of atropine sulfate compared to that of IM atropine sulfate will be assessed based on ratios of least-square means and their associated 90% confidence intervals (CIs) generated from linear mixed models including terms for dosing sequence, route, and period as fixed effects, and subject nested within dosing sequence as a random effect. Bioequivalence will be considered met if the 90% CI of the ratio for AUC_{∞} and AUC_t lie within 80.00 and 125.00%.

Additional details of the statistical analyses, methods, and data conventions will be described in the Statistical Analysis Plan (SAP).

13.1.2.3. Secondary Analyses

The AUC_{45} , AUC_{60} , AUC_{90} , AUC_{120} , AUC_{150} , and AUC_{240} , C_{max} , t_{max} , $t_{1/2}$, λ_z , V_d/F , CL/F , and K_a will also be estimated for each participant and route of administration using the noncompartmental method and will be summarized by route using descriptive statistics. Each parameter will be compared between routes, where applicable, using linear mixed models, including terms for dosing sequence, route, and period as fixed effects, and subject nested within sequence as a random effect in the model. Ratios of least-squares means and associated 90% CIs will be presented.

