5.2. Study Rationale

Nerve agent toxicity requires the rapid administration of antimuscarinic MCMs to mitigate life-threatening bronchospasm and seizures. Rapid administration of centrally acting doses of atropine and anticholinergic medications are most effective within 10 minutes of administration.

Following IV administration of atropine, the heart rate increases within seconds, and the anticholinergic and central nervous system effects may take a few minutes to achieve maximum effect. In contrast, the IM route of atropine administration requires a very high dose before central antimuscarinic effects are seen, and the onset of action is delayed. Further, stockpiled NA MCM configurations (Chempack), containing drugs administered by auto-injector, are insufficient to treat large numbers of NA-poisoned patients in a timely manner. Ophthalmic atropine solution is generally available in the community and may provide a rapid, available source of effective medication in the event of an emergency.

Administration of atropine sulfate ophthalmic solution via the SL route may be an alternative means of delivering a rapid therapeutic dose of atropine to individuals exposed to NA while overcoming the stockpile supply deficits identified above.

The purpose of the current study is to assess the bioequivalence, bioavailability, and PK of SL administered Atropine Sulfate Ophthalmic Solution, USP 1% compared to Atropine Sulfate Injection, USP administered IM in healthy adult volunteers.

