### 11.2.2. Statistical Analysis of Pharmacokinetic Endpoints

PK parameters will be summarized by route of administration using descriptive statistics on the scales outlined below.

For the PK parameters  $AUC_{\infty}$ ,  $AUC_t$ ,  $AUC_{45}$ ,  $AUC_{60}$ ,  $AUC_{90}$ ,  $AUC_{120}$ ,  $AUC_{150}$ , and  $AUC_{240}$ , and  $C_{max}$ , the following will be displayed in the summary table:

- a. Count of subjects with non-missing data for the applicable analysis
- b. Geometric mean
- c. CV% of the geometric mean, which is calculated using the following equation:  
$$\sqrt{10^{\ln(10) \times (SD(\log_{10} value))^2}} - 1 \times 100$$
- d. Minimum and maximum values
- e. Median, and 1st and 3rd quartile values

For the PK parameters  $t_{max}$ ,  $t_{1/2}$ ,  $\lambda_z$ ,  $CL/F$ ,  $V_d/F$ , and  $K_a$  the following descriptive summary statistics will be reported on the untransformed scale:

- a. Count of subjects with non-missing data for the applicable analysis
- b. Arithmetic mean
- c. Standard deviation
- d. Minimum and maximum values
- e. Median, and 1st and 3rd quartile values

Bioavailability of SL administration of atropine sulfate relative to that of IM atropine sulfate will be assessed based on ratios of least-square means and their associated 90% confidence intervals (CIs) generated from linear mixed models to the log-transformed PK parameters including terms for dosing sequence, route (SL or IM), and period as fixed effects, and subject nested within dosing sequence as a random effect. No adjustment will be made for dosing cohort or the interaction for dosing cohort and route.

Ratios of least-squares means of key plasma PK parameters and associated 90% CIs from the linear mixed model will be anti-log transformed to obtain estimates on the original scale.

Bioequivalence will be considered met if the 90% CI of the ratio for  $AUC_{\infty}$  and  $AUC_t$  lie within 80.00 to 125.00%.

Subject specific and population time-concentration profiles on both log and linear scales will be presented. Additionally, PK parameters will be listed by route of administration and subject.

As a supportive analysis of bioavailability, descriptive summary statistics will be displayed in tables for subject-specific ratios between routes of administration.

For each PK parameter, boxplots will be displayed for each route of administration with subject specific lines overlaid.

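### By default the plan compares tmax between routes as a log-scale ratio of least-squares means; a rank-based difference in minutes would suit this near-discrete secondary endpoint better

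*Protocol*

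**What the plan says.** Protocol 13.1.2.3 names tmax with the partial AUCs, Cmax, t1/2, λz, Vd/F, CL/F and Ka. It then states "Each parameter will be compared between routes, where applicable, using linear mixed models" and "Ratios of least-squares means and associated 90% CIs will be presented". It gives no scale for the model and does not say which parameters the where-applicable qualifier leaves out.

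SAP 11.2.2 supplies the scale. The ratios and 90% CIs are "generated from linear mixed models to the log-transformed PK parameters including terms for dosing sequence, route (SL or IM), and period as fixed effects", with subject within sequence as a random effect. It adds: "Ratios of least-squares means of key plasma PK parameters and associated 90% CIs from the linear mixed model will be anti-log transformed". It does not say which parameters count as key.

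The same section separates tmax from the AUCs and Cmax for description. For tmax and five other parameters, "the following descriptive summary statistics will be reported on the untransformed scale": arithmetic mean, SD, median, quartiles, minimum and maximum.

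Protocol section 11 fixes the draws at pre-dose and "13 time points post-dose at 5, 10, 15, 20, 30, 45, 60, and 90 minutes, and 2, 2.5, 4, 6, and 8 hours". SAP section 11 uses actual collection times. SAP section 13 records no change to the tmax analysis.

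**The concern.** Observed tmax is the time of the sample with the highest measured concentration. Actual clock times add a little jitter, but the variable still clusters at 13 values with many ties. A normal model for log tmax is therefore a poor fit, and the default reading of the two documents applies one.

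There is also a bias. After a fast rise the curve falls slowly, so assay error can move the apparent peak to a later sample more easily than to a much earlier one. In relative terms this inflates tmax most for a route that peaks early, and so pulls the between-route ratio toward 1.

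The stake is how the speed of absorption is described. Protocol 5.2 gives a rationale in minutes (treatment is "most effective within 10 minutes of administration"), alongside the supply argument. A ratio of geometric means cannot be read as a delay in minutes, and it could understate the gap between the routes with an interval that is too confident.

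**Working it through.** **The plan's own figures.** None is stated for tmax. The power statement in Protocol 13.2 covers AUC∞ and Cmax only, and it reproduces. With σw = 1.25 × SD × ln(10)/√2 and CV = √(exp(σw²) − 1), SDs of 0.102 and 0.146 give CVs of 0.210 and 0.304 (stated 0.212 and 0.304). The stated CVs with N = 36 give power of 99.4% and 86.0% at a true ratio of 1.0 (stated above 99% and 86%). Nothing below changes these.

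**Is grid spacing the cause?** The steps in ln(time) between successive draws are 0.69, 0.41, 0.29, 0.41, 0.41, 0.29, 0.41, 0.29, 0.22, 0.47, 0.41 and 0.29. After 10 min the grid is roughly even on the log scale. With no assay error, the simulation below gives a bias of only 0-2%. Spacing alone is not the driver.

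**Why error acts upward on an early peak.** Take a one-compartment curve, C(t) ∝ exp(−ke·t) − exp(−ka·t), with assumed ke = 0.0035/min and tmax = ln(ka/ke)/(ka − ke).
- ka = 0.30/min gives tmax = 4.451/0.2965 = 15.0 min. C(5) = 0.760, C(15) = 0.938, C(30) = 0.900. The 30-min sample is 4% below the peak and the 5-min sample is 19% below. A 5% error can easily place the peak at 30 min, a shift of ln 2 = 0.69 in log tmax, but rarely at 5 min.
- ka = 0.12/min gives tmax = 3.535/0.1165 = 30.3 min. C(15) = 0.784, C(30) = 0.873, C(60) = 0.810. Reading the peak at twice its true time now means overcoming a 7% drop, and at half its time a 10% drop. The pull is weaker and more balanced.

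**Simulation.** From the documents: 36 participants and the 13 draws. Assumed: first-order absorption; ke median 0.0035/min (log-SD 0.2); ka median 0.30, 0.20 or 0.12/min for IM and 0.05, 0.03 or 0.02/min for SL (log-SD 0.5), so SL peaks at about 57-105 min; proportional error of 5% or 10%; independent periods; 800 replicates per setting.

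| True IM tmax | Log-model ratio, shift toward 1 | Coverage of 90% CI |
|---|---|---|
| about 15 min | 12-20% | 39-66% |
| about 21 min | 6-14% | 65-85% |
| about 30 min | 3-7% | 83-90% |

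In the same runs the Hodges-Lehmann difference in minutes was within about 5% of truth, with coverage of 82-90%.

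One setting in detail (IM about 20 min, SL about 81 min, 10% error): the true geometric ratio is 3.90 and the model estimate 3.46. Since 3.46/3.90 = 0.887, the ratio is 11% too close to 1; coverage is 0.78. A repeat run gave 3.92, 3.48 and 0.73. The Hodges-Lehmann difference was 60.3 min against a true 60.7 min, with coverage 0.89.

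**Either route.** With SL at about 15 min and IM at about 30 min, the true ratio of 0.50 was estimated as 0.55-0.58 (0.55/0.50 = 1.10, 0.58/0.50 = 1.16), with coverage of 0.69-0.76.

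**A different generating model.** With log-normal true tmax (between- and within-subject SD 0.3 each) and a half-life of 240 min, IM 15/SL 60 min has a true ratio of 4.00. The estimate is 3.94 with no error, 3.44 with 5% error (coverage 0.58) and 3.14 with 10% (0.39). IM 30/SL 60 min has a true ratio of 2.00; the estimates with 5% and 10% error are 1.93 (0.88) and 1.86 (0.84). The pattern is the same. The 5-min first draw matters by itself only for very early peaks: with IM 5/SL 60 min and no error, 12.0 becomes 10.1.

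**The case against.** The strongest reply is that the plan may not model tmax at all. The protocol's where-applicable qualifier, the SAP's restriction of back-transformed ratios to key parameters, and the placing of tmax in the untransformed group all point that way. This stands as an ambiguity. It does not remove the point, because neither document then gives any inferential comparison for tmax. Either way a sentence is missing.

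Second, the only IM peak time in the documents is 30 min (a cited study, Protocol 5.3), where the bias is small. That is fair. The same study, however, reports a 15-min peak for SL injection, and that ordering shows the attenuation with SL as the early route. It concerns injection under the tongue rather than drops, so it does not settle where SL drops will peak.

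Third, the replacement is not better everywhere. When both routes peak at about 30 min, the log ratio was unbiased with 0.90 coverage, while the Hodges-Lehmann interval fell to about 0.82-0.88 because of ties. This also stands.

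Fourth, other rate-related measures are prespecified (AUC45 to AUC240, Cmax, Ka). SAP 11.2.2 also plans the tmax median and range by route, subject-specific ratios and paired boxplots. The tmax model is therefore not the only view of absorption speed, nor is its ratio isolated from everything else reported.

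**Conclusion.** The point holds at modest size. Read together, the two documents by default give tmax a parametric log-scale ratio, with no exemption and no rank-based alternative. Under 5-10% assay error and an earlier peak at about 15-20 min, that ratio is about 6-20% too close to 1 and its 90% CI covers at roughly 0.4-0.85. At 30 min or later the gain from changing is slight. These sizes rest on assumed absorption rates, variability and assay error.

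A reader might infer four stronger things that the documents do not support:
- That the protocol orders a log-scale model for tmax. The log scale is in the SAP only, and both texts carry an undefined qualifier.
- That uneven sampling times cause the bias. Assay error does, with the 5-min floor adding to it for very early peaks.
- That IM is always the route affected, or that the shift is always toward 1. Whichever route peaks early is affected. With very low variability (log-SD 0.08) and no error, 54 of 153 settings moved more than 3% toward 1, 21 moved more than 3% away (up to 12%) and 78 stayed within 3%.
- That the trial's conclusion is at risk. tmax is secondary with no acceptance limit; bioequivalence rests on AUC∞ and AUCt.

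Priority: minor, at the low end of changes that should be made.

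**What to change.** In SAP 11.2.2, state that tmax is excluded from the log-scale mixed model, and list the parameters that remain in it (the AUCs, Cmax and the other continuous parameters). Make the matching change in Protocol 13.1.2.3, or record it in SAP section 13.

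Compare tmax as follows. For each participant take d = tmax in period 1 minus tmax in period 2. In sequence A, d estimates (SL − IM) plus the period effect; in sequence B it estimates −(SL − IM) plus the period effect. The median of all pairwise values (dA − dB)/2 is the Hodges-Lehmann SL-minus-IM difference in minutes, free of the period effect. With 18 evaluable per sequence there are 18 × 18 = 324 such values, and the rank-sum distribution gives the 90% CI. Report it beside the median and range by route already planned.

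The cost is a sentence and a few lines of code before database lock, with no new data. Only participants with both periods contribute, and ties make the interval approximate, most noticeably when the two routes peak at similar times.
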